7.2 Secondary Analysis

The secondary analyses will compare the magnitude of Δ HR from supine to head up tilt (max between 5-10 min of HUTT) with partial compression to no compression and to full compression. Other secondary analyses will include patient reported orthostatic symptoms on tilt with different compression garment configurations, and assessments of other hemodynamic parameters in different garment configurations as well as a regression analysis of orthostatic heart rate and orthostatic symptoms. We will also consider biological sex differences in response to the compression garment. Additionally, co-morbid medical conditions and the medications each participant is prescribed will be evaluated to investigate possible differences in response to the compression garment.

7.3 Sample Size Calculation

Since this is a proof of concept study, there is no preliminary data about the effect of compression on orthostatic HR change in adults. In a pediatric study⁴, the mean orthostatic HR change upon the addition of abdominal and leg compression was about 25bpm. Orthostatic tachycardia is physiologically greater in children and decreases with increasing age, so a more conservative assumption is required. A clinically meaningful reduction in orthostatic tachycardia of 10 bpm would be clinically significant. We estimate a standard deviation of about 15 bpm for our sample. With the aforementioned assumptions for a paired test of continuous data and a 0.05 two-sided significance level, a sample size of 26 POTS patients would allow for 90% power to detect this difference. To account for study withdrawal and dropout we will enroll **40 POTS patients in total**.

8.0 RISKS and INCOVENIENCES

BP cuff: Some may find it uncomfortable to hold their arms with an inflated cuff placed around the forearm, or finger, in a relatively fixed position, or have the cuff inflated frequently.

Electrodes: Sticky patches will be put on your chest and your limbs to record electrical activity from your heart. This might be uncomfortable to you. This can occasionally cause a rash.

Compression Garments: The LifeWrap garment may be uncomfortable to wear.

Tilt-table test (HUTT): There might be light-headedness, dizziness, tremor, headache or nausea during the tilt table test. These symptoms usually resolve rapidly upon lowering of the table.

Transcranial Doppler (TCD): Ultrasound gel will be applied which may cause a rash. The Doppler probe will be in direct contact with the head, which may be uncomfortable. The headband/apparatus will be snug, but there will be opportunities to loosen it off during the recovery periods. Extended use of TCD at a high power may cause tissue heating, however we will keep the TCD at low power, and turn off the data acquisition during recovery periods.

Syncope: A small portion of individuals may experience fainting (syncope) while tilted upright. We will continuously monitor your blood pressure and heart rate and lower you immediately if you faint or request to be lowered. If you faint, you may chose to stop the study or continue with the next tilt table test, if you feel well and are willing.

We cannot foresee any other risks, but there may be previously unknown or unforeseen risks.

9.0 DATA and SAFETY PLAN

9.1 Adverse Event (or Unanticipated Problem) Reporting

Any adverse events of a serious nature will be reviewed immediately with the principal investigator. Serious adverse events will be reported in writing to the CHREB within 10 days of the PI's notification of the event. All study adverse events will be summarized once a year, during the annual review reporting, for the CHREB. The research coordinator will be responsible for tracking adverse events in this study.

The adverse event will be described with the following information: description of the event, outcome of the event, how long it lasted, whether the event required treatment or intervention, and the outcome.

The definition of events is as follows:

Mild – transient and mild in nature, with no treatment necessary.

Moderate – some intervention and treatment necessary, but participant completely recovers.

Severe – an event that results in hospitalization, disability, death or is life threatening.

9.2 Data & Safety Monitor

There will be no external Data & Safety monitor for this study.

10.0 STUDY WITHDRAWAL or DISCONTINUATION

10.1 Principal Investigator Initiated Withdrawal

The principal investigator reserves the right to withdraw the participant from the study after they have provided informed consent, but before study completion. This could occur for one of many reasons, which include, but are not limited to: non-compliance with the protocol, a concern for participant safety, the availability of new knowledge that might affect continued participation in the study, or study termination.

10.2. Study Participant Initiated Withdrawal

Participants are free to withdraw from this study at any time. Withdrawal of consent or refusal to participate will not prejudice their health care.

10.3 Data Post-Withdrawal

If the participant is taken out of the study, or if the participant chooses to no longer be in the study, then we will stop collecting any information on the participant. With the participant's permission we will keep the data already collected, and this will still be used for analysis.

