5.0 ENROLLMENT, RANDOMIZATION and BLINDING

5.1 Recruitment

Patients will be recruited from the Calgary Autonomic Investigation and Management Clinic, and the practices of Drs. [name], [name], and [name], including past research study participants. We will also recruit participants who contact us directly about their interest in our studies.

5.2 Randomization:

Each study participant will complete 4 HUTT on a single day:

- i. one wearing the LifeWrap NASG Garment with all segments fastened;
- ii. one wearing the LifeWrap NASG Garment with the lower leg components fastened;
- iii. one wearing the LifeWrap NASG with the abdominal and pelvic components fastened; and
- iv. one without the garment entirely.

The order of the interventions will be randomized to account for diurnal variation of HR and BP observed in POTS⁹, and any possible training effect with repeated HUTT. Randomization will be performed using a pre-prepared randomization table.

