7.0 STATISTICAL CONSIDERATIONS

7.1 Primary Analysis

The primary analysis will compare the magnitude of Δ HR from supine to head up tilt (max between 5-10 min of HUTT) when the participant is wearing the LifeWrap NASG with full compression applied compared to when the patient has no compression applied. The comparison will use a paired t-test (or a Wilcoxon Signed-Rank test if the data are non-normally distributed).

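### The paired primary test in 7.1 drops anyone who leaves before completing both the full-compression and no-compression tilts; a mixed model on all evaluable tilts would use their data at little cost

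*Combined protocol and SAP*

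**What the plan says.** - **Design (5.2).** "Each study participant will complete 4 HUTT on a single day": full compression, lower leg only, abdomen and pelvis only, and no garment. On order: "The order of the interventions will be randomized to account for diurnal variation of HR and BP observed in POTS". A possible training effect is also given as a reason. The sequences in the randomisation table are not described.
- **Primary analysis (7.1).** The heart-rate rise on tilt (ΔHR, using the maximum from minutes 5 to 10) is compared "when the participant is wearing the LifeWrap NASG with full compression applied compared to when the patient has no compression applied". The test is a paired t-test, or a Wilcoxon signed-rank test if the data are not normal.
- **Leaving between tilts.** Section 8.0 tells participants: "If you faint, you may chose to stop the study or continue with the next tilt table test". Section 10.2 allows withdrawal at any time, and 10.1 allows the investigator to withdraw someone.
- **Data after withdrawal (10.3).** On withdrawal, "then we will stop collecting any information on the participant". What was already gathered is covered by: "With the participant's permission we will keep the data already collected, and this will still be used for analysis".
- **Sample size (7.3).** 26 patients are needed. "To account for study withdrawal and dropout we will enroll" 40.

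No section defines an analysis set, a rule for incomplete pairs or a method for missing tilts.

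**The concern.** Both tests named in 7.1 work on within-person differences. A participant who leaves before one of the two key tilts has no difference and falls out of the primary comparison, even if the other key tilt was recorded. Whether that happens depends on the random order and on what made the person leave.

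The second part could bias the result. The hypothesis in 3.1 expects more tachycardia and symptoms without compression. Someone who has a bad no-compression tilt first and then stops is lost from the primary test. Someone with the same bad tilt after the full-compression tilt is kept. The retained pairs can therefore under-represent large no-compression responses and understate the benefit. The 14 extra participants protect power but do nothing about this selection.

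**Working it through.** **1. The plan's own figure.** Inputs from 7.3: difference 10 bpm, SD 15 bpm, two-sided 0.05, power 90%. Taking 15 as the SD of the paired difference, the noncentral-t calculation (noncentrality = (10/15)·√n, n − 1 df) gives power 0.892 at n = 25 and 0.904 at n = 26. The stated 26 is reproduced. The allowance is 40 − 26 = 14, and 14/40 = 35%. Power is 96.9% with 35 pairs and still 90.4% with 26, so power is not the issue.

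**2. Who enters the paired test.** Assume all 24 orders are equally likely. After k tilts, P(full and none both done) = C(k,2)/C(4,2).

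| Leaves after | Pair complete | At least one of the five planned ΔHR comparisons (7.1, 7.2) usable |
|---|---|---|
| 1 tilt | 0/6 = 0% | 0% |
| 2 tilts | 1/6 = 16.7% | 5/6 = 83% |
| 3 tilts | 3/6 = 50% | 100% |

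The 5/6 arises because, of the six possible pairs of conditions, only leg versus abdomen is not among the planned comparisons.

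**3. Dependence on order.** Suppose a participant stops right after a no-compression tilt in position 1, 2 or 3. The pair survives only if full compression came earlier, with probability 0, 1/3 or 2/3. The average is 1/3.

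**4. Size of the bias when the triggering tilt is recorded.** The documents give no withdrawal or syncope rate, so this is illustrative.

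- *Scenario A.* 40 participants; true reduction 10 bpm; SD of differences 15. Assumed: mean ΔHR 40/36/32/30 bpm for none/leg/abdomen/full; within-person correlation 0.3 to 0.7; withdrawal with probability 0.5 to 1 after a tilt above 50 bpm, or certain above 55. On average 27 to 35 pairs remain. Across repeated runs the paired estimate averages 9.0 to 9.9 bpm. A mixed model on all completed tilts averages 9.8 to 10.1, with a standard error within about 0.07 bpm of the paired test's.
- *Scenario B.* Assumed means 40/35/33/30, SD 15 per condition, correlation 0.5, certain withdrawal after a tilt above the threshold:

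| Threshold (bpm) | Pairs kept, of 40 | Paired estimate (bpm) |
|---|---|---|
| 70 | 0.978 × 40 = 39.1 | 9.8 |
| 60 | 0.904 × 40 = 36.2 | 9.5 |
| 55 | 0.831 × 40 = 33.3 | 9.5 |
| 50 | 0.726 × 40 = 29.0 | 9.2 |

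The shortfall is therefore 10 − 9.9 = 0.1 to 10 − 9.0 = 1.0 bpm. For comparison, the standard error of the paired mean is 15/√35 = 2.5 bpm with 35 pairs and 15/√27 = 2.9 bpm with 27.

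If withdrawal is purely random (10% after each tilt), the gain from the model is a standard error about 2 to 3% smaller.

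**5. Does the model need period?** Under correlation 0.5, certain withdrawal above 50 bpm and an assumed trend of −3 or +3 bpm per period, a model with condition only averages 9.6 or 10.5. Adding period gives 10.1 in both cases.

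**6. When the triggering tilt has no endpoint.** Same setting without the trend, model with condition only:

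| Triggering tilt | Paired | Model |
|---|---|---|
| Recorded | 9.4 | 10.1 |
| Half have no value | 8.7 | 9.0 |
| None has a value | 8.0 | 7.5 to 7.6 |

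**The case against.** A reader might infer that 10.3 makes a promise that 7.1 breaks. The text does not support that. Section 10.3 speaks of analysis in general, and 7.2 plans partial-compression comparisons, symptom and haemodynamic analyses and a heart-rate–symptom regression, several of which can use an incomplete participant. Nor is it telling that most of a withdrawn person's tilts go unused in the primary test: a full completer also has only two of four tilts in it.

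A reader might also infer that 14 withdrawals are expected, or that the primary result is in serious danger. The 14 is headroom for all withdrawal and dropout, not a forecast for a single session of about four hours. The bias found is small and towards no effect, and at a 70 bpm threshold it nearly vanishes.

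The strongest objection concerns mechanism. The one explicit link in the documents between a bad tilt and stopping is fainting (8.0). Under 6.2.4 a tilt ends at syncope or on request, and the endpoint in 6.3 needs minutes 5 to 10. If the tilt ended before 5 minutes it has no value, and step 6 shows the model then does no better than the paired test and can do slightly worse. This objection stands and limits what the change can achieve. It does not cover someone who faints after 5 minutes, or who finishes an unpleasant tilt and then leaves. Those tilts have a value, and the paired test may still discard it.

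**Conclusion.** The point holds as a cheap improvement, at the level of something to consider; it is not a contradiction in the documents. As written, the primary test takes in 0, 1/6 or 1/2 of participants who leave after one, two or three tilts, given equally likely orders. If leaving follows a large recorded ΔHR, the paired estimate is too small by roughly 0.1 to 1.0 bpm against 10 bpm, less than its standard error. A mixed model on all evaluable tilts removes most of that at essentially the same precision. These sizes rest on assumed condition means, correlations and withdrawal rules, and on 15 bpm being the SD of the paired difference, which 7.3 does not state. They do not extend to tilts without a 5 to 10 minute value.

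**What to change.** In 7.1, make the primary estimate of full versus no compression come from a linear mixed model with condition and period as fixed effects and participant as a random effect. Fit it to every tilt with an evaluable 5 to 10 minute ΔHR from every randomised participant, including those who withdraw and permit use of their data. Period belongs in the model because 5.2 expects diurnal and training effects and withdrawal unbalances period across conditions.

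Keep the paired t-test, with its signed-rank fallback, on complete pairs as a sensitivity analysis. Report the number withdrawing by the condition of the preceding tilt.

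The cost is analysis wording only: no change to procedures, visits or sample size. The downsides are slightly more modelling, a little precision spent on the period terms, and validity that rests on withdrawal depending only on recorded tilts. The change does not repair the bias from tilts that end before 5 minutes, and the plan should say so.

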11.0 COMPENSATION

Participants will be financially compensated for parking costs related to this study. Participants will not be financially compensated for their time involved in this study. We are doing assessments that might generate knowledge about their medical condition and may indirectly be of benefit to them.

12.0 PRIVACY and CONFIDENTIALITY ISSUES

Protected Health Information will be used in this study. The investigators will comply with the patient privacy guidelines of the University of Calgary and applicable provincial and federal rules.

The research team is comprised of experienced research nurses and research assistants who are aware of the importance of confidentiality of health information. Paper research records will be stored in a locked office. Digital records will be stored on password-protected University of Calgary computers/servers and in the University of Calgary Clinical Research Unit REDCap Database.

Every effort will be made to publish and present the data from this study. At no time will any participant be identified in any such publication.

13.0 FOLLOW-UP AND RECORD RETENTION

13.1 Follow Up

There is no follow-up in this study. Once the physiological study day has been completed, the participant will be finished in this protocol. We may approach participants who participate in this study for further studies related to POTS.

14.0 Study Sponsor

Departmental Funds and the start-up package of [name] [name] will support this study. We may later apply for independent funding.

